#### 5.3 Study Endpoints

## 5.3.1 Primary Endpoint

The primary effectiveness outcome measure for the current study will be the physician global assessment (PGA) of "0" or "1" indicating clear or minimal disease according to the following classification:

| Score   | Category | Description                                                           |
|---------|----------|-----------------------------------------------------------------------|
| 0 Clear | Clear    | Plaque elevation = 0 (no elevation over normal skin)                  |
|         |          | Scaling = 0 (no scale)                                                |
|         |          | Erythema = $\pm$ (hyper pigmentation, pigmented macules, diffuse      |
|         |          | faint pink or red coloration)                                         |
| 1       | Minimal  | Plaque elevation = $\pm$ (possible but difficult to ascertain whether |
|         |          | there is a slight elevation above normal skin)                        |
|         |          | Scaling = $\pm$ (surface dryness with some white coloration)          |
|         |          | Erythema = up to moderate (up to definite red coloration)             |

| Score   | Category | Description                                                           |
|---------|----------|-----------------------------------------------------------------------|
| 2       | Mild     | Plaque elevation = slight (slight but definite elevation, typically   |
|         |          | edges are indistinct or sloped)                                       |
|         |          | Scaling = fine (fine scale partially or mostly covering lesions)      |
|         |          | Erythema = up to moderate (up to definite red coloration)             |
|         | Moderate | Plaque elevation = moderate (moderate elevation with rough or         |
| 3 Moder |          | sloped edges)                                                         |
|         |          | Scaling = coarser (coarse scale covering most of all of the lesions)  |
|         |          | Erythema = moderate (definite red coloration)                         |
|         | Severe   | Plaque elevation = marked (marked elevation typically with hard or    |
|         |          | sharp edges)                                                          |
| 4       |          | Scaling = coarse (coarse, non tenacious scale predominates            |

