## 6.1 Selection of Study Population

Patients will be enrolled from the offices of community dermatologists across Canada treating patients with Psoriasis. The sample of physicians invited to participate in the study will be selected in a way that it is a random representative sample of the Canadian population and distribution of dermatologists.

All patients with psoriasis treated at the participating centers will be potentially eligible

to be included in the study. Those fulfilling the study inclusion and exclusion criteria will be invited to participate in the study by the site investigator or designee. Treatment will be according to the treating physician's judgment and routine care and must adhere to the product monograph and regional regulatory requirements. Use of medications for the management of psoriasis that is off—label or not in accordance with existing regulations will not be permitted. Prior to inclusion in the study all patients will be required to sign a written informed consent agreeing to allow use of their data in the study. Since this is not an interventional study and patients are treated as per routine care the purpose of the informed consent will be to allow the use of the data and contact of the patients by the study personnel as required. The study protocol, informed consent, questionnaires and participating physicians will be approved by a central or local independent ethics review board as required by regional or institutional regulations.

Changing the patient's treatment including initiation of treatment with adalimumab must be exclusively the treating physician's decision and must be reached prior to patient screening and enrollment and has to be entirely independent of the conduct of the study. The observational nature of the study dictates that all treatments used in the current study, including adalimumab, must be prescribed as per routine care and in accordance to the Canadian and provincial marketing authorization and criteria.

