#### 6.2 Number of Patients to be Enrolled

A total of 660 patients will be enrolled in the current study from the practices of 30-40 dermatologists. A maximum of 30 patients per site will be allowed. Recruitment will be over a 24 month period. In order to provide adequate power to assess the effect of different treatment modalities, it will be recommended that 50% of the patients from each site will be initiated on treatment with adalimumab.

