### 3.2 Bias by Indication

One of the most important challenges in conducting between treatment comparisons in observational or naturally occurring experiment studies is confounding by indication. This occurs because the patients are allocated to different treatment groups not randomly but on the basis of the treating physician's judgment. This may result in an imbalance of the prognostic profile between the treatment groups and therefore confounding in the assessment of differences with respect to the study outcome measures. Multi-variable models that include potential confounders as covariates or propensity scores developed with potential confounders are valid solutions for the statistical adjustment of between group baseline differences and minimization of bias. The development of the propensity score will be based on categorical or multinomial logistic regression and binary logistic regression for the assessment of the profile differences between patients treated with adalimumab, topical agents and traditional systemic agents. Stratification of the analyses into homogeneous subgroups is another solution. All of these solutions will be explored in the current study. Unfortunately determination of the appropriate approach is data driven and cannot be determined a-priori.

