## 3.8 Subject Demographics and Baseline Characteristics

Descriptive statistics consisting of the mean, median, standard deviation and 95% confidence interval of the mean for continuous scale variables and frequency distributions for categorical variables will be produced for the baseline characteristics. These descriptive

COMPLETE - PS Statistical Analysis Plan Version 3.0 July 23rd, 2015 Page 28 of 231

statistics will be produced for the study cohort as a whole and for the three treatment cohorts as described in section 2.4, and by Canadian regions.

Between-group differences with respect to baseline characteristics will be assessed for statistical significance with One Way Analysis of Variance (ANOVA) for continuous variables if normally distributed or the Kruskal Wallis test if not normally distributed, and the Chi-Square statistic or the Fisher's exact test for categorical variables. Variables for which a trend for statistical significance (P<0.15) or clinically important difference (more than 2–fold) is observed will be considered as potential confounders and will be included as covariates in the multivariable analyses or propensity score development described in the following sections.

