## 3.10 Analysis of the Primary Objective

For the primary objective, between-group differences with respect to achieving a PGA of "0" or "1" at six months will be assessed with simple logistic regression analysis and multivariate logistic regression models adjusting for potential confounders or the propensity score. In addition, a Generalized Estimating Equation (GEE) model will be used to compare

COMPLETE - PS Statistical Analysis Plan Version 3.0 July 23rd, 2015 Page 30 of 231

the three patient groups in terms of achieving a PGA of "0" or "1" over 24 months of treatment. Kaplan Meier based time to event (survival) analysis will be used with the log-rank test to assess the statistical significance of the between group differences. Cox's proportional hazards model will also be used to adjust for potential confounders or the propensity score.

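### No site or physician term is named in the month-6 logistic, GEE or Cox models, although the treating physician both chooses the treatment and rates the PGA

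*SAP*

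**What the plan says.** The primary analysis is "simple logistic regression analysis and multivariate logistic regression models adjusting for potential confounders or the propensity score" (SAP 3.10). A GEE over 24 months, Kaplan-Meier curves and a Cox model accompany it. Covariates come from a screen of baseline characteristics: "Variables for which a trend for statistical significance (P<0.15) or clinically important difference" of more than 2-fold (SAP 3.8). On how to adjust, SAP 3.2 says: "Unfortunately determination of the appropriate approach is data driven and cannot be determined a-priori".

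The visible text does not make site or physician a fixed effect, random effect, stratum, propensity-score variable or cluster. In the SAP methods, site number appears only as a sort key for listings (3.1.1). The titles of Tables 48-50 and 52 mention only treatment group, possible confounders or propensity scores.

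On structure, Protocol 6.2 says: "A total of 660 patients will be enrolled in the current study from the practices of 30-40 dermatologists". It adds: "A maximum of 30 patients per site will be allowed". It also says "it will be recommended that 50% of the patients from each site will be initiated on treatment with adalimumab", which is a recommendation only. Changing treatment "must be exclusively the treating physician's decision" (Protocol 6.1). The endpoint is a physician rating: "The primary effectiveness outcome measure for the current study will be the physician global assessment" (Protocol 5.3.1). The treating physician collects the clinical data (Protocol 6.5), and no independent assessor is described.

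**The concern.** SAP 3.2 traces confounding by indication to the physician's judgment, but the adjustment it describes uses patient characteristics. Two things can go wrong when the same physicians prescribe and grade.

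- **Variance.** Patients graded by one physician resemble each other. If cohort mix also differs between sites, a model that treats patients as independent gives standard errors that are too small.
- **Bias.** If physicians who use more adalimumab also grade more leniently, or have easier patients, the between-site part of the comparison enters the treatment odds ratio. Patient covariates can remove some of the case-mix part, but not the leniency part.

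At stake is the primary contrast of adalimumab with the other cohorts. The systemic-versus-topical contrast is also exposed: the study is meant to detect it (Protocol 10.3), and the 50% recommendation does not balance it.

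**Working it through.** **Plan's own figure.** There is none for clustering. Neither Protocol 10.3 nor SAP 2.7 contains a design effect.

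**Cluster size** (Protocol 6.2 and 10.3). 660/40 = 16.5 and 660/30 = 22 enrolled per dermatologist. With 25% attrition, 0.75 × 16.5 = 12.4 and 0.75 × 22 = 16.5 evaluable.

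**Variance by formula.** For m evaluable patients per site, outcome ICC ρ and treatment intraclass correlation ρx, the design effect is DE = 1 + (m − 1)·ρ·ρx. The true type I error of a nominal 5% test is 2[1 − Φ(1.96/√DE)]. The documents give neither ρ nor ρx, so both are assumed.

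- Exact 50:50 in every site: ρx = −1/(m − 1), so DE = 1 − ρ. At ρ = 0.05, DE = 0.95 and type I error is 4.4%, slightly conservative.
- ρx = 0.2, ρ = 0.05, m = 16.5: DE = 1 + 15.5 × 0.05 × 0.2 = 1.155, type I error 6.8%.
- Extreme, one treatment per site (ρx = 1): at ρ = 0.05, DE = 1.57 (m = 12.4) to 1.77 (m = 16.5), type I error 11.8-14.1%.

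**Simulation with no treatment effect.** 33 sites × 15 evaluable patients = 495 = 0.75 × 660; adalimumab versus the rest; 6,000 runs; plain logistic model without covariates. Spread is the SD of site prescribing on the logit scale. Correlation is between a site's tendency to record good PGA and its tendency to prescribe adalimumab.

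| Scenario | ICC 0.05: OR, type I error | ICC 0.10: OR, type I error |
|---|---|---|
| Exact 50% in every site | 1.00, 3.9% | 1.00, 4.1% |
| SD 1, correlation 0 | 1.00, 6.0% | 1.00, 7.1% |
| SD 2, correlation 0 | 1.00, 7.6% | 1.00, 10.2% |
| SD 1, correlation 0.3 | 1.11, 10.6% | 1.15, 13.5% |
| SD 1, correlation 0.5 | 1.18, 16.0% | 1.26, 25.9% |

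The ORs are exponentials of the mean log OR, for example exp(0.229) = 1.26. A test stratified by site stays at 4.2-5.5% in all these rows. A second simulation with 35 sites × 14 patients agrees: 4.3-5.1% at 50% per site, 5.6-9.6% with varying prescribing, and a null OR of 1.11-1.26 with type I error of 10-25% under correlation 0.3-0.5.

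**Systemic versus topical.** With exactly 50% adalimumab in every site and a systemic/topical split that varies, correlation 0.3-0.5 gives a null OR of 1.11-1.28 (ICC 0.05) or 1.15-1.40 (ICC 0.10), with type I error of 7-27%. Meeting the 50% recommendation therefore does not protect this contrast.

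**Cost of full stratification.** At OR (0.50/0.50)/(0.36/0.64) = 1.78, where 36% is the mean of the planned 40% and 32%, and ICC 0.05, power falls from about 85% to 77% (SD 1) and from 84% to 65% (SD 2).

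**The case against.** **No inflation is shown for the design the protocol recommends.** This stands. With 50% adalimumab at every site the plain standard errors for adalimumab versus the rest are about right or slightly too large. A reader might infer that the planned error bars are wrong; the documents do not support that. They leave it open, because the recommendation is not binding and the site mix is unknown.

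**The bias needs assumptions.** This also stands. Nothing in the documents gives an ICC or shows that leniency tracks prescribing. The simulations are unadjusted, and the planned covariates or propensity score would deal with part of any case-mix difference.

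**Site could still be included.** The phrase about potential confounders does not exclude it, SAP 3.2 mentions stratified analyses, and SAP 3.1.1 promises table footnotes listing covariates. The mock tables were not in the text available. So the claim is only that the visible text does not name site. The GEE and mixed models do not fill the gap: they are described for outcomes over time, unequal visit times and missing visits.

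**Adjusting for site is not a cure.** A reader might infer that within-site comparison removes the whole problem at little cost. It does not. A physician who grades adalimumab patients more favourably than their other patients does so within the site, where site adjustment cannot reach. Patient-level confounding by indication also remains and can weigh more: if unmeasured severity raises adalimumab use (log-odds 1.0 per SD) and lowers response (−0.7 per SD), a true OR of 1 is estimated at 0.64 without site and about 0.58 with stratification. That is a reason to show both analyses.

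**The cap is per site.** A site may have more than one dermatologist, so 30 is not a cap per rater.

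**Conclusion.** The point holds as a conditional one. No site or physician term is named for the month-6 logistic, GEE or Cox models, while prescriber and rater are the same person. Standard errors may be too small, and the contrast may absorb physician differences, if cohort mix varies between sites.

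For adalimumab versus the rest, type I error is about 4-5% with 50% adalimumab everywhere, and about 6-10% at ICC 0.05-0.10 with logit SD 1-2. With leniency correlated 0.3-0.5 with adalimumab share at SD 1, the null OR is about 1.11-1.26 and type I error about 10-26%. ICC, spread and correlation are all assumed. The documents show neither that the bias exists nor its direction. They do show that the plan, as visible, would neither detect nor remove it.

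**What to change.** In SAP 3.10:

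- Prespecify a site random intercept in the month-6 logistic model, with the site's cohort mix (its adalimumab and systemic shares) as covariates, alongside the patient-level confounders or propensity score. The intercept alone would leave part of the between-site difference in the treatment estimate.
- Account for site in the GEE (site-level clustering) and the Cox model (site clustering or frailty). Clustering corrects the standard error only, so carry the cohort-mix covariates there too.
- Report cohort mix by site. This shows readers which row of the table above the study is nearest to.
- Give the fully site-stratified (conditional) logistic analysis as a sensitivity analysis, and keep the model without site beside it.
- State that none of this addresses differential grading within a site or unmeasured patient severity.

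The change is SAP wording; the site number is already on every CRF section (Protocol 9.0). The statistical cost is precision. Once cohort mix is in the model, the treatment effect rests largely on within-site comparisons, so the loss can approach that of full stratification. It is greater for systemic versus topical: in the three-cohort simulation, stratification raised the SD of the log OR by 19-43% there, against 6-12% for adalimumab versus systemic. Sites that contribute a single cohort add little.

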## 3.11 Analysis of the Secondary Objectives

Between groups differences with respect to the changes in the BSA, PGA, DLQI, PASQ, BDI, SF-36 WLQ from baseline to 24 months of treatment will be assessed with One Way ANOVA or repeated measures, mixed effects general linear model adjusting for potential confounders or the propensity score. Planned contrasts will be used to assess between group differences at the other follow up time points. Pairwise between group comparisons will be adjusted for multiplicity with the Tukey's Least Significance Test.

In order to better assess the impact of the treatment received and changes in the regimen the treatment will be handled as a time-dependent covariate in these analyses. Descriptive statistics will be used to assess the between-group differences in healthcare resource utilization and healthcare costs associated with PS. With respect to achieving therapeutic response end points and incidence of articular and extra-articular manifestations between group differences will be assessed with multivariate logistic regression while Cox proportional hazard models will be used to assess between group differences with respect to the time of achieving therapeutic response and first occurrence of articular and extra-articular manifestations.

Descriptive statistics will be used to assess the regional differences with respect to baseline patient characteristics and disease parameters. Descriptive statistics will also be used to assess the practice patterns of Canadian dermatologists in the management of patients with

### COMPLETE - PS Statistical Analysis Plan Version 3.0 July 23rd, 2015 Page 31 of 231

moderate to severe Plaque PS. The study cohort will be divided into Canadian regions as Quebec, Ontario, Maritimes and Western Canada.

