In Canada, the Canadian Expert Drug Advisory Committee (CEDAC) of the Canadian Agency for Drugs and Technologies in Health has recommended adalimumab in the treatment of psoriasis under the following conditions:

- i. Patient is diagnosed with severe debilitating psoriasis; and
- ii. Body surface involvement of more than 10% and / or significant involvement of the face, hands, feet or genital areas; and
- iii. Failure to respond to, contraindication or intolerance to methotrexate and cyclosporine; and
- iv. Failure to respond to, intolerant to or unable to access phototherapy.

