#### 10.2 General Considerations:

Descriptive statistics consisting of the mean, median, standard deviation and 95% confidence interval of the mean for continuous scale variables and frequency distributions for categorical variables will be produced for the baseline characteristics. These descriptive statistics will be produced for the study cohort as a whole and for the three treatment cohorts as described in section 6.0.

Between cohort differences with respect to the baseline parameters will be assessed with the Chi-Square statistic for categorical variables and One Way Analysis of variance (ANOVA) for continuous scale variables. Variables for which a trend for statistical significance (P < 0.15) or clinically important difference (more than 2 - fold) are observed will be considered as potential confounders and will be included in the multivariate analyses or propensity score development described later. Descriptive statistics will be produced for all variables and the changes from baseline when Statistical Methods to Address the Study Objectives:

Between group differences with respect to achieving the primary effectiveness outcome, specifically a PGA of "0" or "1" at 24 months will be assessed with simple logistic regression analysis and multivariate logistic regression models adjusting for potential confounders or the propensity score. A more relevant analysis will be to assess the differences between the groups with respect to the time to achieving the end point. For this analysis Kaplan Meier based time to event (survival) analysis will be used with the log-rank test to assess the statistical significance of the between group differences. Cox's proportional hazards model will also be used to adjust for potential confounders or the propensity score.

Between groups differences with respect to the changes in the BSA, PGA, DLQI, Psoriasis

Related Pruritus Assessment VAS, Plaque Psoriasis and Psoriatic Arthritis Pain VAS, BDI,9SF-12 (second version) WLQ from baseline to 24 months of treatment will be assessed with One Way ANOVA or repeated measures, mixed effects general linear model adjusting for potential confounders or the propensity score. Planned contrasts will be used to assess between group differences at the other follow up time points. Pairwise between group comparisons will be adjusted for multiplicity with the Tukey's Least Significance Test.

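### Secondary change scores may be tested by an unadjusted one-way ANOVA instead of the adjusted mixed model, with no rule for choosing, in a comparison that is not randomised

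*SAP*

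**What the plan says.** SAP 3.11 covers changes in BSA, PGA, DLQI, PASQ, BDI, the SF health survey and WLQ. These changes "from baseline to 24 months of treatment will be assessed with One Way ANOVA or repeated measures, mixed effects general linear model", and the sentence goes on to adjustment for confounders or the propensity score. Protocol 10.2 has a similar list and the same choice, with the ANOVA followed by "or repeated measures, mixed effects general linear model adjusting for potential confounders or the propensity score". Neither document gives a selection rule or ranks the two results.

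Other parts of the plan bear on the choice:

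- SAP 3.2 states that patients are "allocated to different treatment groups not randomly but on the basis of the treating physician's judgment". On how to adjust for this it says: "Unfortunately determination of the appropriate approach is data driven and cannot be determined a-priori".
- Under SAP 3.8, baseline variables that differ between cohorts at P<0.15, or by more than 2-fold, "will be considered as potential confounders and will be included as covariates in the multivariable analyses or propensity score development".
- SAP 3.3 and 3.4 rely on mixed models to deal with unequal visit times and missing visits.
- SAP 3.11 adds that "the treatment will be handled as a time-dependent covariate in these analyses".
- SAP Table 53, on burden of illness, names only the mixed model. No listed table title names an ANOVA.

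Neither document names the month-0 value of the outcome as a fixed covariate.

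**The concern.** A one-way ANOVA has treatment group as its only factor, so the adjustment phrase can apply only to the mixed model. The wording therefore permits an unadjusted comparison of physician-selected cohorts for all the listed measures. That is the bias SAP 3.2 warns about.

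The ANOVA also drops everyone without a month-24 value, in a study that expects 25% attrition, and it cannot take treatment switches into account.

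A further problem is specific to change scores. Baseline enters the ANOVA only by subtraction. If patients with higher scores tend to fall further whatever they receive, a cohort that starts worse shows a larger mean change. There are grounds to expect unequal starts. The Canadian advisory recommendation cited in Protocol 3.0 lists severe debilitating disease among its conditions for adalimumab, together with "Body surface involvement of more than 10% and / or significant involvement of the face, hands, feet or genital areas; and" failure of, or unsuitability for, methotrexate and cyclosporine. Study entry asks only for moderate or severe disease. The choice between two analyses that can disagree in this way should not stay open until the data are seen.

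**Working it through.** The documents give no effect size, SD or power for the secondary change scores, so there is no stated figure to reproduce. The check asks how often the one-way ANOVA rejects when the treatments are equally effective.

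**Inputs from the documents.** Enrolment is 330:165:165 with 25% attrition (SAP 2.7). 330 × 0.75 = 247.5 and 165 × 0.75 = 123.75, so 248:124:124 is used (N = 496). Alpha is 0.05, two-tailed (SAP 3.1.1).

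**Assumptions, not in the documents.** The adalimumab cohort starts D baseline SDs worse than the topical cohort, and the systemic cohort lies midway. Follow-up = a + b × baseline + error, with the same a and b in every cohort, so treatment has no effect. The within-cohort SD is 1 at both visits.

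**Formulas.**

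- Mean change in a cohort, relative to topical: (b − 1) × its baseline gap.
- Variance of change within a cohort: (b − 1)² + (1 − b²).
- Noncentrality: λ = Σ n(mean change − overall mean)² / variance.
- Rejection rate: the probability that a noncentral F(2, 493, λ) exceeds the 5% critical value.

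**One case in full: D = 0.50, b = 0.5.**

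- Mean changes are −0.25, −0.125 and 0, with weighted mean 0.5 × (−0.25) + 0.25 × (−0.125) = −0.15625.
- Deviations are −0.09375, 0.03125 and 0.15625.
- The variance is 0.25 + 0.75 = 1.
- λ = 248 × 0.00879 + 124 × 0.00098 + 124 × 0.02441 = 5.33, and the rejection rate is 52.8%.

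**All cases.** Each cell gives the spurious extra improvement, adalimumab versus topical, and the ANOVA false-positive rate.

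| D (SD) | b = 0.3 | b = 0.5 | b = 0.7 |
|---|---|---|---|
| 0.25 | 0.175 SD, 21.2% | 0.125 SD, 16.2% | 0.075 SD, 11.5% |
| 0.50 | 0.350 SD, 68.2% | 0.250 SD, 52.8% | 0.150 SD, 33.8% |
| 0.75 | 0.525 SD, 96.4% | 0.375 SD, 88.1% | 0.225 SD, 66.5% |

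Simulation with 4,000 runs per cell agrees with the table. In the same runs, a model with the baseline value as covariate rejects in 4.2% to 5.8%, and its spurious gap is about zero.

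**Two cases that go the other way.**

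- With b = 1, every patient improves by the same absolute amount. The ANOVA stays at 5.0% with no bias.
- If each cohort regresses to its own stable mean (D = 0.5, reliability 0.5), the change-score ANOVA is unbiased (4.8%). Baseline adjustment then rejects in 65% of runs, with a spurious gap of 0.25 SD against the more severe cohort.

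**How often SAP 3.8 would bring in the baseline score.** Apply a three-group test of baseline at P<0.15 to 248:124:124. λ is 5.33, 21.31 and 47.95 for D = 0.25, 0.50 and 0.75, and the rule is met in 73%, 99.8% and more than 99.9% of studies.

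**The case against.** The plan leans towards the mixed model. The same sentence offers adjustment, SAP 3.3 speaks of mixed models as the ones to be used, Table 53 names only that model, and a one-way ANOVA cannot meet the plan's own time-dependent treatment requirement. A reader might infer that the sponsor means to report the unadjusted test. The documents do not show that. The fair description is an unresolved alternative. It still has to be resolved, because Table 53 covers burden of illness only and the text allows either result to be presented.

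SAP 3.8 already covers much of the baseline problem within the adjusted model. If the outcome's own baseline score counts as a baseline characteristic, it would usually qualify, as the last calculation shows. This stands for the mixed model. It does nothing for the ANOVA, and at small gaps it leaves the covariate to chance.

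A reader might also infer that adalimumab is bound to be favoured on most secondary outcomes. The documents do not support this:

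- They give no baseline severity by cohort.
- The cited conditions are advisory, and the body-surface condition can be met through the site of involvement.
- All cohorts enter on the same severity criterion.
- Failure of earlier systemic drugs could make the adalimumab cohort harder to treat, which would push the other way.
- Nothing shows that BDI, the SF survey or WLQ differ between cohorts at baseline.

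Finally, conditioning on baseline is not free of risk, as the second counter-case shows. The treatment decision must precede screening (Protocol 6.1), so the recorded questionnaire scores did not themselves determine it. This objection stands, and it is why the fix includes a sensitivity analysis.

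**Conclusion.** The point holds as a defect of specification. Both documents permit an unadjusted test of month-24 change in non-randomised cohorts, next to an adjusted model, with no rule between them. That option conflicts with SAP 3.2 to 3.4 and with the treatment handling in SAP 3.11.

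The size is conditional. The range of about 12% to 96% rests on the assumed gaps, the assumed slopes and post-attrition sizes of 248:124:124. A slope below 1 is plausible, because patients enter when treatment is being changed and BSA, PGA and DLQI cannot fall below zero, but the documents do not give it. The percentages show what the ANOVA can do. They are not estimates of what it will do in this study. The primary analysis in SAP 3.10 is not affected. The change should be made, since it is cheap and removes an avoidable source of bias.

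**What to change.** 1. In SAP 3.11 and Protocol 10.2, delete the one-way ANOVA option, or keep it and label it descriptive only.
2. Name the repeated-measures mixed model, adjusted for the confounders or propensity score, as the main analysis. Take the month-24 contrast and those at the other visits from that model.
3. Include the month-0 value of each measure as a covariate by default, whether or not it meets the P<0.15 rule.
4. Add one sensitivity analysis: the same adjusted model for change without the month-0 covariate. Agreement would show that the result does not depend on the choice. Disagreement should be reported as such.
5. Settle whether WLQ is collected at month 0. Protocol Table 1 shows no baseline WLQ, while SAP Table 1 does. Without it, neither a change from baseline nor the covariate exists for that measure.

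The cost is edits to both documents and a small amount of extra analysis. Apart from the WLQ question, the data are already scheduled.
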